All AEs (AE or SAE) will be recorded on the AE study documents. For participants who have an ongoing AE at their final study visit, follow-up information will be captured in the AE eCRF page which will be completed after 30 days.

Serious Adverse Event Follow-Up

For all ongoing SAEs occurring during the study, the Investigator must submit follow-up reports regarding the participant's subsequent course. All SAEs that are ongoing at the end of the study or upon discontinuation of the participant's participation must be followed until either:

- The event resolves, or
- The event/condition has stabilized (e.g., in the case of persistent impairment), or
- The event returns to baseline, if a baseline value is available, or
- The participant dies, or
- The event can be attributed to other than the study beverage, or to other than the study conduct.

CONDUCT OF THE STUDY

1. Ethics and Regulatory Considerations

This study will be conducted according to Good Clinical Practice Guidelines, the Declaration of Helsinki (2004) and United State Code of Federal Regulation Title 21. Signed written informed consent for participation in the study will be obtained from all participants before protocol-specific procedures are carried out. Participants will be

informed of their right to withdraw from the study at any time. Participants will be informed that their participation in the study is completely voluntary, personal information will be both deidentified to preserve anonymity.

2. Institutional Review Board

The Investigator will ensure that an appropriately constituted IRB, in compliance with the requirements of 21 CFR 56, reviews and approves the clinical study. Before the study is started, the Investigator will forward copies of the protocol and consent form for this study to the IRB for review and approval. IRB approval must refer to the study by exact protocol title and number, identify the documents reviewed, and state the date of review. The IRB must be informed of all subsequent protocol amendments. No alterations, modifications to IRB-approved documents, including the protocol, protocol summary, consent form, recruitment materials and questionnaires will be allowed. The IRB must also be informed of all SAEs and of unexpected AEs as outlined in the IRB's SOPs or reporting guidelines.

3. Informed Consent and Protected Health Information

The study will be explained verbally as well as on the informed consent document. Each participant will be given ample opportunity to inquire about details of the study and to read and understand the consent form before signing it. It will be made clear that participants can withdraw from the study at any time.

Each participant's signed informed consent document must be kept on file by the Investigator. The participant should receive a copy of the informed consent document. A participant may not be admitted to the study unless informed consent of the participant (or his/her legally authorized representative) has been obtained.

4. Participant Confidentiality

The Investigator is responsible for ensuring that participants' anonymity will be maintained. For all the data collected over the course of the study for each participant (i.e. records, biological samples and questionnaires) a unique subject identifier (i.e. a code) will be assigned and used instead of the subject's name. The code for each participant which links the subject name with their identifier will only be available to research personnel. Electronic CRFs or other documents will identify participants by initials, number, or code, and not by name. The Investigator will keep a separate log showing codes, names, and addresses. Any records that contain the subject's name and identifier will either be stored in the Kinesiology file storage room in a file cabinet (locked) or protected on a computer via password protection on the individual digital file and password protection on the computer the file(s) are stored on. All other records that contain the subject identifier only will also be kept in either a file cabinet in our locked file storage room or on a password protected computer. Subject names will never be used in

any presentation or publication resulting from this study. The records will be maintained until the data are published and up to a maximum of ten years after the completion of the study. All records or biological data obtained after signing of the informed consent (including the screening visit, even for subjects that are not eligible for participation in the study) are treated with the same confidentiality safety measures as those subjects who qualify. Any information obtained during the prescreening for participants that were not eligible will be deleted

5. Withdrawal of Participants from the Study

Participants may be removed from the study for any of the following reasons:

- A participant requests discontinuation;
- The Investigator initiates removal for medical or compliance reasons;
- Occurrence of any AE or condition that could, in the Investigator's opinion, interfere with the evaluation of the effect of the study beverage or put the participant at undue risk.

It is understood by all concerned that an excessive rate of withdrawals can render the study uninterpretable, therefore, unnecessary withdrawal of participants should be avoided. Should a participant decide to withdraw, all efforts will be made to complete and report observations as thoroughly as possible. In the event that a participant is withdrawn from the study, the reason for the withdrawal will be documented in the eCRF.

References

5. Myette-Côté É, Caldwell HG, Ainslie PN, Clarke K, Little JP. A ketone monoester drink reduces the glycemic response to an oral glucose challenge in individuals with obesity: a randomized trial. *The American Journal of Clinical Nutrition*. 2019;110(6):1491-1501.

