Figure 1| Metabolism of 3 ketone ester compounds and the BDO ketone-precursor.

IMPACT

KEs could represent a practical STAK method that does not require any change in diet. However, there is a critical need to elucidate unique attributes of the many new exogenous ketone compounds and how their metabolism varies between individuals to inform KE use in the field. This high impact project will contribute important knowledge that aims to develop next-generation KE molecules and formulations that are designed to meet the needs of operators at different points in their career. Our long-term goal is to create evidence-based guidelines for deployment of diverse KE compounds, dose level, and timing based on individual characteristics and operational/training requirements.

RESEARCH STRATEGY

This is an open label, randomized, placebo controlled, 9-arm crossover study where healthy adult men (n = 15) will consume four different exogenous ketone products at two serving sizes or a non-ketogenic placebo (one study product per test day). Data/sample collection will include blood (capillary and whole venous blood), gas exchange measures, urine, heart rate/variability and study product tolerability.

OUTCOMES

Primary

- Difference in total plasma ketone appearance (AUC) between the two serving sizes of study products and control

Secondary*

- Differences in other blood ketone kinetic parameters (peak concentration, time of peak concentration, AUC of different ketone bodies, capillary ketone concentrations).
- Differences in urine and breath ketone excretion
- Differences in blood metabolites (glucose, free fatty acids, alanine).
- Differences in heart rate and heart rate variability and blood pressure
- Differences in subjective tolerability and subjective satiety measured by questionnaires
- Differences in blood hormones (insulin, ghrelin).
- Differences in blood acid-base balance (bicarbonate, strong ions
- Differences in respiratory gas exchange (VO₂ and VCO₂)

*All comparisons will be made between the two serving sizes of one study product and vs. control.

PARTICIPANTS

This study aims to recruit a homogenous, military relevant population to remove the confounding effects of variation in phenotype on exogenous ketone metabolism as far as possible. Thus, we will 15 recruit healthy and normally-active resistance/endurance trained men from the ages of 20-30 yr that represents typical active-duty military

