Participants will then consume the Study Product that they were randomly allocated for that Test Day (details of Study Products below). Time of ingestion should be +/- 60 minutes from the time established at Test Day 1; they will be given 5 minutes to consume the Product. After Study Product consumption, they will remain at the study center for ~4h, with blood and breath sampling occurring at regular intervals (see Figure 2). A total of 7 whole blood samples (7x ~8 mL each= ~56mL) will be collected each Test Day. Capillary blood samples and breath acetone readings will be collected at the same time as whole blood samples. The fitted face mask will be worn for 10 minutes each hour to collect respiratory gas measures. Participants will be asked to collect all urine passed during the test in a provided container, and asked to fully void their bladder and collect the urine at the end of the test day. Participants will complete satiety questionnaires each hour, and will complete a BTQ at the end of the Test Day.

Participants will be asked to minimize ambulatory movement during the Test Day. Non caloric beverages (i.e.,water) will be permitted *ad libitum* and intake volumes will be recorded. At the end of each Test Day, the heart rate monitor and IV cannula will be

removed and a dressing will be applied to the cannula site. Participants will be given a snack to consume.

Sample Processing and Analysis

Blood Processing: Whole blood collected through the IV cannula will be either 1) immediately stabilized for AcAc analysis using a validated method, 2) processed to plasma (EDTA tubes), or 3) serum (clot activator serum collection tubes) and then snap frozen in liquid nitrogen for storage prior to analysis (details below). We will collect capillary blood samples for real-time analysis of blood BHB and glucose concentration, using commercially available test strips and a handheld monitor (KetoMojo, CA, USA), this will also allow comparison of ketone values obtained via different methods.

Blood Sample Analytical Methods:

- *Ketones* will be determined by multiple methods to provide a robust measure of ketosis and allow cross validation. Firstly: by capillary BHB concentrations obtained from a finger stick using a handheld device (KetoMojo, USA). Secondly: plasma ketones (AcAc, R-BHB and S-BHB) will be measured using ultra-performance liquid chromatography – tandem mass spectrometry (LC-MS). Thirdly: Continuous Ketone Monitoring (see details below)

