Statistical Plan. Statistical analysis of data will take place on completion of the study in collaboration with Buck Bioinformatics Core. Participant data will be included if they have completed at least 2 serving sizes of one exogenous ketone product AND the control Test Days (i.e., BHB- mono-ester 180 mg/kg, BHB mono-ester 360 mg/kg and Control). Any incomplete exogenous ketone compounds (i.e., participant completed C6 Di-ester 180 m/kg and AcAc ester at 360 mg/kg) will be excluded from the analysis. All decisions regarding exclusion from the analysis population will be documented prior to database lock. Missing data will not be imputed, and only observed data will be included in the statistical analysis.

Repeated measure group x time ANOVA (or a non-parametric alternative) will be performed following initial tests to ensure sphericity is not violated. We will compare data between control group vs. each individual exogenous ketone at both doses (i.e., control vs BHB-mono ester (180 mg/kg) vs BHB-mono-ester (360 mg/kg). We will also test for condition x time interactions. If significance is detected, post-hoc comparisons will be made using Tukey's HSD tests (or non-parametric alternative) to correct for multiple comparisons. Significance will be accepted at an alpha level of P < 0.05.

Other data processing:

- Area Under the Curve (AUC) will be calculated using the Trapezoid Rule.
- Maximal/minimal concentration data (C_{max} and C_{min}) and time of maximal/minimal concentration (T_{max} and T_{min}) will be extracted from the raw data.

- A composite tolerability score is calculated by adding the scores (0 -3, corresponding to none, mild, moderate, severe) of all ten listed symptoms.

STUDY MONITORING

Concomitant Medication/Supplements and Treatment

All concomitant medications/supplements used 1 months prior to Screening Visit and during the study will be reported to the study personnel for assessment and recorded in the participant's study documents.

Adverse Event Monitoring

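### Time of peak ketone concentration is to be tested against a non-ketogenic control, where it has no kinetic meaning, and the control also weakens the comparison of the two servings

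*Protocol*

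**What the plan says.** The secondary outcomes in the Protocol (OUTCOMES, Secondary) include "Differences in other blood ketone kinetic parameters (peak concentration, time of peak concentration, AUC of different ketone bodies, capillary ketone concentrations". The footnote to that list applies to every item on it: "All comparisons will be made between the two serving sizes of one study product and vs. control". Under RESEARCH STRATEGY, participants take "four different exogenous ketone products at two serving sizes or a non-ketogenic placebo".

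The Statistical Plan repeats the three-way structure: "We will compare data between control group vs. each individual exogenous ketone at both doses". Comparisons within that set come second: "If significance is detected, post-hoc comparisons will be made using Tukey's HSD tests (or non-parametric alternative) to correct for multiple comparisons". Under Other data processing, "time of maximal/minimal concentration (T_{max} and T_{min}) will be extracted from the raw data".

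Nothing in the Protocol exempts Tmax from the comparison with control, and nothing says what Tmax means for a profile without a peak. A statistical analysis plan may exist and is not at hand, but one that follows the Protocol inherits this comparison.

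**The concern.** Tmax describes how quickly a product delivers ketones. After a non-ketogenic drink there is no delivery to time. The highest of the day's values will fall wherever noise puts it if fasting ketones are flat, near the last sample if they drift up, and near the first if they drift down. Testing an active serving against that number compares a kinetic property with an artefact.

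There is a second effect. The useful question is whether the peak moves between 180 and 360 mg/kg of one compound. The Statistical Plan reaches it only as a follow-up to a test that contains the control. The control's arbitrary Tmax therefore helps decide whether the follow-up is done, and in a pooled analysis it helps set the error term.

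The IMPACT section names timing as one aim of the eventual guidelines, and Tmax is the listed outcome that speaks to it most directly. The same structure is repeated for all four products.

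**Working it through.** **Inputs from the Protocol.** Evaluable n = 12 (Sample Size); three conditions per product; significance at P < 0.05; Tukey follow-up only after a significant overall test (Statistical Plan). Testing Days gives "A total of 7 whole blood samples" over about 4 h. The planned 15 follows from 12/(1 − 0.20) = 15. The 12 was derived for AUC; the Protocol gives no figure for Tmax to reproduce.

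**Assumptions not in the Protocol.** Samples at 0, 30, 60, 90, 120, 180 and 240 min (the actual times are in a figure not shown). Tmax for an active serving is 30, 60 or 90 min with probability 0.3, 0.5 and 0.2. A true shift adds 30 min for the larger serving. Control ketones are flat at 0.15 mM, rising from 0.10 to 0.20 mM, or falling in mirror image, with 15% noise.

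**Step 1: hand calculation, flat control.** Control Tmax has mean about 103 min and SD about 77 min.

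- Active mean = 0.3×30 + 0.5×60 + 0.2×90 = 57 min.
- Active variance = 0.3×900 + 0.5×3600 + 0.2×8100 − 57² = 3690 − 3249 = 441, so SD = 21 min.
- With independent values, the pooled error mean square for three conditions is (77² + 441 + 441)/3 = (5929 + 882)/3 ≈ 2270.
- Tukey statistic for a 30-min shift: 30/√(2270/12) = 30/13.75 ≈ 2.2, against a critical value of about 3.55 (3 means, 22 df).
- Paired t on the two servings: 30/√(882/12) = 30/8.57 ≈ 3.5, against about 2.20 (11 df).

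The control's scatter alone moves the expected statistic from well above its threshold to well below it.

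**Step 2: simulation under the same assumptions.**

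| Share of trials | Flat control | Rising | Falling |
|---|---|---|---|
| Control vs 180 mg/kg declared different (Tukey) | about 40% | 100% | 73-75% |
| 30-min shift found: ANOVA, then Tukey | 5% | 60% | 73% |
| 30-min shift found: Friedman, then Bonferroni-Wilcoxon | 44% | 63% | 64% |
| 30-min shift found: paired t, two servings only | about 90% | about 90% | about 90% |
| Same paired t, Bonferroni for three comparisons | about 74% | about 74% | about 74% |
| Equal servings: false serving difference (Tukey) | 0-1% | 0-1% | 0-1% |

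The paired rows do not use the control. In the first row the product is the same throughout, and only the control's behaviour changes the answer.

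**Step 3: a different model.** Smooth concentration curves with 10% noise gave control Tmax, mean (SD), of 103 (77) min flat, 232 (18) rising and 17 (23) falling. Control vs active was declared different in 3-52%, 100% and 68-100% of runs respectively. For true peaks at 45 and 75 min, power for 180 vs 360 mg/kg with control in the model, against the unadjusted paired test, was 0.06 vs 0.85 (flat), 0.77 vs 0.84 (rising) and 0.73 vs 0.84 (falling). Across all true shifts tried with a drifting control, the loss ran from about 1 point (97.6 − 96.2) to about 16 points (39.5 − 23.8).

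**The case against.** Several counter-arguments have force.

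- **The analysis is not fixed as pooled ANOVA with Tukey.** The Statistical Plan calls for a sphericity check and allows a non-parametric alternative. With a flat control, Mauchly's test rejected sphericity in 92-93% of simulated trials, so the 5% figure belongs to a method the plan would often set aside. This stands. The non-parametric route tried still found the shift in only 44-64% of trials.
- **The 90% comparator is unadjusted.** With Bonferroni for three comparisons it is about 74%, essentially the same as Tukey with a falling control (73%). This stands as a like-for-like comparison. If control is left out, however, each product has only one Tmax comparison, and no adjustment within the product is needed.
- **The overall test may be significant although the servings are equal.** That is no fault: a three-condition test should reject when control differs.
- **The comparison of servings is already required.** True, but the Statistical Plan reaches it only through the test that includes control.
- **The consequence is small.** Tmax is one parameter within one secondary bullet, and a careful reader may discount a Tmax read from a near-flat profile. This limits the weight of the point but does not make the contrast meaningful.

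A reader might infer that the plan manufactures Tmax differences between servings. It does not: with equal servings the rate was 0-1%. Nor does the Protocol state that control is flat or lacks a peak. It says only that the placebo is non-ketogenic.

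**Conclusion.** The point holds in a limited form. The Protocol requires a Tmax contrast with control that cannot be interpreted as product kinetics, whichever way fasting ketones move. This needs only the inference that a non-ketogenic drink produces no product-driven peak.

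The loss of power for 180 vs 360 mg/kg is secondary and conditional. It is severe if control Tmax is scattered and its variance enters a pooled error term. With a drifting control it is moderate to small, and against an adjusted paired test it can be close to nil. All these figures rest on assumed sampling times, noise and Tmax distributions.

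It would be tempting to conclude that the trial's main result is compromised, or that 5% power is what to expect. The documents support neither. The primary AUC comparison with control is meaningful and unaffected, and 5% is the worst of the cases examined. The change is worth making because it costs nothing and sharpens the only Tmax comparison that can be interpreted.

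**What to change.** Amend the OUTCOMES footnote and the Statistical Plan with one sentence, for example: *Time of peak blood ketone concentration will be compared only between the two servings of the same product, by a paired test or its non-parametric equivalent; control will not enter that model, and its time of peak will be reported descriptively, if at all.* Keep the control contrasts for AUC and peak concentration, where the control value has a clear meaning. Confine the sentence to blood ketones, since time of peak is not a named outcome for breath.

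The cost is one sentence in two places. No data, visits, samples or participants are added, and the only comparison removed is one that could not be interpreted.

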bowel disease, irritable bowel syndrome, chronic constipation, severe constipation (in the opinion of the Investigator), history of frequent diarrhea, history of surgery for weight loss, gastroparesis, systemic disease that might affect gut motility according to the Investigator, medication managed reflux and/or clinically important lactose intolerance].

- Participant has a condition the Investigator believes would interfere with his ability to provide informed consent, comply with the study protocol, which might confound the interpretation of the study results, or put the participant at undue risk.

Sample Size. Our primary outcome goal is to demonstrate significant differences between serving sizes of exogenous ketone compounds in plasma total ketone AUC. Previous work using the BHB Monoester compared to ketone salt products demonstrated that a sample size of 12 participants was required to detect a difference in BHB AUC of ~20% (80 mM.h⁻¹) between ketone compounds with alpha set at 0.5 and power at 0.8. This sample size will also give sufficient power to address our secondary aims which include differences in peak ketone concentrations, plasma BHB, AcAc, breath acetone, glucose, insulin, free-fatty acids, amino acids, blood chemistry, pH, gas exchange values and heart rate. Based upon prior studies, we expect up to 20% of participants will withdraw from the study after recruitment, and therefore we will plan to recruit 15 participants.

Recruitment:

Recruitment will occur through well-established methods at OSU, which include word of mouth, ResearchMatch database, social media engagement and flyers. For this study we will specifically aim to recruit cadets in the OSU Reserve Officers Training Corps (ROTC), who have participated in research on ketosis in the past and been supported by their cadre to enroll in our research projects (see letters of support from Army, Navy, and Air Force ROTC leadership).

Randomization:

If a participant meets all inclusion and none of the exclusion criteria, the following will occur at the end of the screening visit:

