NJ, USA) and ‘Avela’ (Genomatica, CA, USA), respectively. The AcAc Diester is commercially available (on Amazon <https://www.amazon.com/KetoLogic-Ketone-DiEster-Softgels>) and is currently being used in clinical studies of Angelman’s Disease²¹. We have been in communication with the companies that produce these exogenous ketones to ensure product availability and support for this work (see letters of support from BHB Therapeutics/Juvenescence and Disruptive Nutrition).

Quality Control: As only small amounts of product are needed for this study, and products are shelf stable, our aim is that all product inventory will be acquired at the start of the study to ensure the same product lots are used throughout. We plan to obtain Certificates of Analysis to confirm product exogenous ketone content.

Serving Size Rationale: Previous work has shown that lean body mass (LBM) is a major covariate in KE responsiveness⁹. Therefore, we will standardize exogenous ketone serving sizes to LBM (assessed using DXA) for all trials at 180 and 360 mg/kg LBM, which for a participant with 70 kg of lean mass corresponds to ~12.5 and 25 g, respectively. These serving sizes are representative of typical commercial serving sizes and are expected to elevate blood BHB in the range of 1.5 - 2 mM^{22,23}.

Blinding: It will not be possible to completely blind study participants or investigators due to visible differences between the C6 Ketone Di-ester and BHB-Mono-ester beverages and also the capsule delivery form for the AcAc Di-ester. However, study products will be coded (A, B, C, D and CON), and data analysts will remain blinded to the coding until analysis is complete.

Storage: The study products will be stored in a dry secure location at ambient temperature (15- 77°F) and are best served chilled. Study product supplies are to be used only in accordance with this protocol and under the supervision of the Investigator.

Table 1: Study product details

Study Active Ingredient	Serving Sizes	Form	Other product ingredients [ALLERGENS]	Example Commercial Product (Company)
BHB Mono-ester	180 mg/kg and 360 mg/kg	Ready to drink beverage	Water	DeltaG Tactical (TDeltaS Global, FL, USA)

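### The sample-size paragraph prints alpha as 0.5 against a 0.05 decision rule, gives the AUC difference in an impossible unit, and borrows its power from a different endpoint and contrast

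*Protocol*

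**What the plan says.** The Sample Size paragraph (Protocol, PARTICIPANTS) opens with its goal: to show "significant differences between serving sizes of exogenous ketone compounds in plasma total ketone AUC". It then justifies the number from elsewhere: "Previous work using the BHB Monoester compared to ketone salt products demonstrated that a sample size of 12 participants was required". The target of that earlier calculation is printed, with its unit, as a "difference in BHB AUC of ~20% (80 mM.h⁻¹". Its error rates are stated for a contrast "between ketone compounds with alpha set at 0.5 and power at 0.8". The paragraph goes on to say, without figures, that the same number is adequate for a list of secondary measures. It allows for 20% withdrawal and so recruits 15.

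Four other places bear on this:

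- **OUTCOMES, Primary:** "Difference in total plasma ketone appearance (AUC) between the two serving sizes of study products and control".
- **Statistical Plan:** "Significance will be accepted at an alpha level of P < 0.05". AUC is computed by the trapezoid rule. Each product is analysed at both servings together with control, with Tukey post-hoc comparisons.
- **Serving Size Rationale:** the servings "are expected to elevate blood BHB in the range of 1.5 - 2 mM".
- **Testing Days:** after the product, "they will remain at the study center for ~4h".

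**The concern.** Four things in one paragraph do not fit the rest of the protocol.

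1. The alpha of the calculation is ten times the alpha of the analysis.
2. The effect is given as concentration per hour, but a trapezoid AUC is concentration multiplied by time.
3. The calculation answers a different question from the primary outcome: a different analyte (BHB, not total ketones), a different contrast (between compounds, not between servings and against control), and a comparator, ketone salts, that is not a study product.
4. The secondary-power claim has no effect size or SD behind it for any measure.

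Because this paragraph is the sole basis for 12 evaluable participants, a reader can neither reproduce that number nor say what difference the primary comparison could detect. A null result between servings would then be hard to interpret.

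**Working it through.** **The plan's own figures.** The attrition step reproduces: 12 / (1 − 0.20) = 15. The 12 does not, because no SD, within-person correlation, sidedness or test is stated. One can only solve backwards for what 12 would imply.

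**Alpha.** Assume a two-sided paired t-test with n = 12. Power = P(|T| > t(1−α/2; 11)), where T is noncentral t with 11 df and noncentrality d√12, and d = mean difference / SD of the within-person difference. Solving for 80% power:

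| alpha | d for 80% power | SD implied by a difference of 80 |
|---|---|---|
| 0.5 | 0.43 | 80/0.4256 = 188 |
| 0.05 | 0.89 | 80/0.8887 = 90 |

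Only if 0.5 was really used would d = 0.43 be the design effect; power for it at 0.05 would then be about 27%. The document cannot settle which alpha was used, because it prints no SD.

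**Unit.** A difference of 80 that is about 20% implies a reference AUC of 80/0.20 = 400.

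- As mM.h over about 4 h: 400/4 = 100 mM on average. Against 1.5 to 2 mM this is 100/2 = 50 to 100/1.5 = 67 times too high.
- As mM.min over 240 min: 400/240 = 1.67 mM, inside the expected range.

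Removing the exponent to give mM.h therefore does not repair the figure. Minutes would, but the dose and sampling window of the earlier study are not given, so this stays a conjecture until the source is checked.

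**Planned contrast.** The protocol gives neither the difference nor the SD for total ketone AUC between servings or against control, so both are assumed here. The assumptions are units of mM.min, n = 12, two-sided 0.05, one normally distributed AUC per condition, and sphericity. For Tukey over three conditions (control and two servings), error df = (3−1)(12−1) = 22, q = 3.553, and the critical t is 3.553/√2 = 2.512. The effect detectable with 80% power rises from 0.89 to 0.98 SD.

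Power, paired t (Tukey in brackets):

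| Difference | SD 90 | SD 120 | SD 150 |
|---|---|---|---|
| 80 | 80% (71%) | 56% (44%) | 39% (28%) |
| 120 | 99% (98%) | 88% (82%) | 71% (61%) |
| 160 | >99% (>99%) | 99% (98%) | 92% (87%) |

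**Fewer than 12 for a product.** The Statistical Plan includes participants product by product, so some comparisons may have fewer than 12. The effect detectable with 80% power is then 0.94 SD (Tukey 1.03) at n = 11 and 1.00 SD (Tukey 1.08) at n = 10.

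**The case against.** The strongest reply is that nothing here shows an underpowered trial. The alpha is almost certainly a misprint and changes no test, since the Statistical Plan governs at 0.05. The unit is probably a mislabel for minutes. The comparison with 100 mM applies this trial's window and expected level to another study, and the protocol does not say whether 1.5 to 2 mM is a mean or a peak. The primary contrasts involve a doubled serving and a non-ketogenic control, so differences well above 20% are plausible. The table stops at 160, or 40% of the implied reference, and uses no SD below 90. Under the same assumptions, a difference of 200 with SD 150 has 99% power (Tukey 98%), and a difference of 80 with SD 70 has 95% (Tukey 92%). Sidedness and the detail of multiplicity may sit in an unseen SAP.

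Most of this stands as a limit on the conclusion. Low power is not shown, the 27% is conditional on a reading nobody need believe, and sidedness and Tukey detail are not defects in themselves. It does not remove the point. The protocol itself states the justification, states it with a wrong alpha and a wrong unit, and rests it on an endpoint and contrast other than the ones its first sentence names. That larger differences are plausible is an argument the paragraph should make with figures, and it does not.

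**Conclusion.** The concern holds, and the paragraph should be corrected. Alpha 0.5 contradicts the 0.05 decision rule, and mM.h⁻¹ cannot be an AUC unit; both are probably slips without effect on any test. The mismatch of endpoint and contrast does not depend on either slip: the 80% power quoted belongs to a different question, and the protocol gives no SD or expected difference for its own. Under the assumed ranges, n = 12 may be ample or short (28% to above 99% under Tukey), and the document does not let anyone tell. The step from 12 to 15 is right. The claim of sufficient power for the secondary aims is unsupported as written. Confidence is high on the textual contradictions; no claim is made that 12 is too few.

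**What to change.** Retrieve the source calculation and rewrite the paragraph:

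- State alpha 0.05 and whether it is two-sided. If 0.5 was really used, say so and restate the power at 0.05 (about 27% for the same effect, two-sided paired t-test).
- Correct the AUC difference and its unit from the source; write mM.min only if the source confirms it.
- Give the within-person SD from prior data and the difference expected in total ketone AUC, between servings and against control.
- Confirm 12 for those contrasts under Tukey, or state the power that 12 delivers.
- Delete the general claim for the secondary aims, or limit it. For a single summary value per participant, with 12 complete for the comparison, there is 80% power for a paired difference of about 0.89 SD at two-sided 0.05, or about 0.98 SD with Tukey over three conditions, assuming normality and sphericity. Add that this does not cover the group-by-time or non-parametric analyses.

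The cost is one paragraph and the retrieval of one prior calculation with its SD. The numbers stay at 12 evaluable and 15 recruited. The price is a less favourable statement: power for the primary contrast may have to be restated, and the blanket secondary claim goes.
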